## 6.7 Short-acting medications

Use of the following medications, which are not rescue medications, only results in efficacy data at the next scheduled visit being treated as missing/non-response:

- Higher than Baseline dose of nonsteroidal anti-inflammatory drugs (NSAIDs) and cyclooxygenase-2 (COX-2) inhibitors, including as needed (PRN) use within 72 hours prior to scheduled study visit (Note: No intake at baseline is considered equivalent to a baseline dose of 0).
  - Higher than Baseline dose of analgesics or opioids including PRN use within 48 hours prior to scheduled study visit (Note: No intake at baseline is considered equivalent to a baseline dose of 0).
- Any increase in dose of oral corticosteroids within 7 days prior to scheduled study visit (Note: The increase has to be higher than baseline).

Confidential

All medication data resulting in efficacy data being treated as missing/non-response will be flagged in the concomitant medication listing.

## 6.8 Medical procedure history and concomitant medical procedures

All medical procedures, in history or concomitant, will be presented in data listings. The historical procedures with no start date will be assigned to Reduced CZP dose (for those study participants who started the study taking Reduced CZP) or Original CZP dose (for those study participants who started the study taking Original CZP).

The ratios of compliance will be summarized as a continuous variable and categorically (eg. 0 - <0.80, 0.8 - 1.0 and >1.0). Treatment compliance will be summarized and listed for the SS for the Reduced CZP Dose, Original CZP Dose, and Any CZP Dose for the final analysis; for

Confidential Page 44 of 252 the Updated week 24 Interim Analysis, treatment compliance was summarized and listed for the SS for the Reduced CZP Dose and Original CZP Dose.

concentrations and anti-CZP antibodies analyzed using the ECLIA methods. In addition, PK and ADAb samples (for which sufficient volume is available) collected in this study prior to Protocol Amendment 9, will be analyzed with the ECLIA methods.

Data from the ECLIA methods, that are within the stability coverage and constitute the study's main PK and ADAb evaluations be listed. As such, PK and ADAb evaluations are proved.

reported only in study participant listings.

### 8.1 **CZP** plasma concentrations

Only CZP plasma results analyzed using the ECLIA method will be summarized using the participants in the PK-PP set. CZP plasma concentrations are measured at Baseline, Weeks 1, 4, 12, 16, 17, 24, 32, 40, 48, every 24 weeks thereafter, the Early Discontinuation/EOT Visit, and the Final Visit; for study participants enrolled prior to Protocol Amendment 8, samples were not collected after implementation of Protocol Amendment 8. CZP plasma concentrations will be summarized by CZP dose (Original CZP Dose, Reduced CZP Dose) using geometric means, 95% CIs for the geometric mean, geometric CV, and the median, minimum and maximum concentrations.

The geometric CV will be calculated using the following formula:

$$geoCV(\%) = \sqrt{\exp(SD^2) - 1} * 100$$

where SD=standard deviation from the log-transformed data.

For the two CZP Dose groups, summaries at all available visits and plots of plasma concentration results will be produced separately by Baseline weight group, Baseline age group, ADAb participant status classification, ADAb titer classification (see Section 8.2) and, concomitant MTX use in combination with Baseline weight group.

Line-plots will be produced to summarize geometric mean (+/- 95% CI) plasma concentration over time. On each plot there will be separate plot lines for each subgroup category as described above. Plasma concentration will be plotted on both linear and semi-logarithmic scales.

In addition, spaghetti plots of CZP plasma concentrations over time will be produced for individual study participants, separately for each CZP dose group. Plots will be provided by Baseline age group, Baseline weight group, concomitant MTX use in combination with Baseline weight group. In each plot, different symbols/colors will be used to identify subgroup categories.

Concentrations below the limit of quantification of 320.0 ng/mL (0.32µg/mL) (BLQ) will be replaced by the LLOO divided by 2 for the calculation of descriptive statistics. The geometric

Confidential Page 45 of 252 mean and CV% will be derived when at least two-thirds of the concentrations at a certain visit are above the LLOQ and not missing. A minimum of 3 values are required to calculate summary statistics. If only 2 values are available then these should be presented as the minimum and maximum with other descriptive statistics reported as missing ("-") When the mean value includes one or more replaced BLQ values then a footnote should be included to say "contains one or more BLQ value replaced by half the LLOQ value". If the criteria are not met, only the maximum and minimum values will be shown. Similarly, the 95% CI of the geometric mean will be calculated if at least 5 samples are available at a time point.

All summaries will be provided for the PK-PP Set. All plasma concentration data will be listed. Concentrations should be listed to the same number of significant figures supplied by the bioanalytical laboratory. For listings concentrations below the limit of quantification should be reported as BLQ (below the limit of quantification).

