#### 2.2 Study variables

#### 2.2.1 **Primary variables**

## Pharmacokinetic and immunological variables 2.2.1.1

- CZP plasma concentrations at Weeks 16 and 48
- Anti-CZP antibody levels at Weeks 16 and 48 (

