Based on 24-week interim results from the first 163 study participants enrolled in RA0043, both the Original CZP Dose and Reduced CZP Dose showed safety profiles similar to the approved CZP dose in the adult RA population. The overall clinical response in this analysis (taking both doses into account) was PedACR30 and PedACR50 responses of 77.3% and 67.5%, respectively at Week 12. The response from the original dose was 75.6% for PedACR30 and 64.1% for PedACR50; the response from the reduced dose was 78.8% for PedACR30 and 70.6% for PedACR50. PedACR50 response demonstrates a highly clinically relevant decrease in disease activity.

Therefore, in order to adequately assess the exposure levels and clinical experience of CZP in pcJIA at both the Reduced and Original CZP Doses and support the safety for the Original CZP Dose, as more of the safety data collected in the study prior to Amendment 9 were on the reduced dose, 30 additional study participants have been enrolled on the Original CZP Dose following Protocol Amendment 9.

All study participants enrolled following Protocol Amendment 9 will have plasma concentrations of CZP and anti-CZP antibodies analyzed using the ECLIA method. In addition, PK and ADAb samples (for which sufficient volume is available) collected in this study prior to Protocol Amendment 9 will be analyzed with the ECLIA method. The collective ECLIA-based PK data for this study will form the basis of any future CZP PK analysis, and was the basis for the modeling and simulation work that supported the interim PK analysis in 2023 and the 2024 submission.

Full interim analyses were performed in 2016 after all active study participants completed the Week 24 (Visit 10) assessments. Week 24 full interim analyses were completed as described in SAP Amendment 1. An Updated Week 24 (Visit 10) interim analysis, including the 30 new study participants enrolled after Protocol Amendment 9, was completed as described in SAP Amendments 4, 5, and 6. The final analysis will be completed as described in SAP Amendment 6.

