#### 8.1.1 **ECLIA vs ELISA samples**

In line with the proportion of study participants and the proportion of PK samples with sufficient volume for re-analysis with the ECLIA method out of all PK samples initially analyzed with the ELISA method were summarized for the Updated Week 24 Interim analysis only.

First, the number and percentage of study participants with at least one PK sample reanalyzed using the ECLIA method (after previous analysis using the ELISA method) were presented. For this percentage, the denominator is the number of study participants with at least one non-missing PK result from the ELISA method, and the numerator is the number of study participants with at least one non-missing PK result from the ECLIA method that had also been analyzed with the ELISA method previously. (Below LLOQ is considered a nonmissing result.)

Second, the number and percentage of post-baseline PK samples that were re-analyzed using the ECLIA method (after previous analysis using the ELISA method) were presented. For this percentage, the denominator is the number of post-baseline PK samples with non-missing ELISA results. The numerator is the number of post-baseline PK samples with non-missing ECLIA results where the same PK sample had previously been analyzed using the ELISA method. (Below LLOQ is considered a non-missing result.)

Additionally, the proportion of study participants and the proportion of PK samples with sufficient volume for re-analysis with the ECLIA method out of all PK samples analyzed with the ECLIA method (either originally or via re-analysis) were summarized.

First, the number and percentage of study participants with at least one PK sample reanalyzed using the ECLIA method (after previous analysis using the ELISA method) were presented. For this percentage, the denominator is the number of study participants with at least one non-missing PK sample that was analyzed using the ECLIA method (either originally or via re-analysis). The numerator is the number of study participants with at least one non-missing PK result from the ECLIA method for a sample that had also been analyzed with the ELISA method previously. Also, the number and percentage of study participants that did not have any PK sample re-analyzed with the ECLIA method were presented. The denominator is the same, but the numerator is the number of study participants for whom all

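### The two-thirds rule for CZP geometric means can count missing assay results as failures, and when it fails it also drops a median that can still be estimated

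*SAP*

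**What the plan says.** SAP Section 2.2.1.1 names "CZP plasma concentrations at Weeks 16 and 48" as a primary variable. Section 8.1 restricts the summaries to ECLIA results in the PK-PP Set and plans them by dose "using geometric means, 95% CIs for the geometric mean, geometric CV, and the median, minimum and maximum concentrations". The same summaries are repeated by weight group, age group, ADAb status, ADAb titer class, and MTX use combined with weight group.

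BLQ values (LLOQ 0.32 µg/mL) are replaced by the LLOQ "divided by 2 for the calculation of descriptive statistics". Section 8.1 then sets the display rule for the geometric statistics: "mean and CV% will be derived when at least two-thirds of the concentrations at a certain visit are above the LLOQ and not missing". It also asks for at least 3 values for summary statistics and at least 5 samples for the CI. It closes with "If the criteria are not met, only the maximum and minimum values will be shown". The words on missingness entered with SAP Amendment 6 (Section 13.6, Change #25).

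On where missing results come from, Section 2.3 says "PK and ADAb samples (for which sufficient volume is available) collected in this study prior to Protocol Amendment 9 will be analyzed with the ECLIA". Section 8.1.1, when counting re-analysed samples, keeps the two states apart: "Below LLOQ is considered a nonmissing result".

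**The concern.** The rule puts two different things through one test. A BLQ result is information about exposure. A result missing because the archived tube was nearly empty is not. If both fail the test, a visit can lose its geometric mean because of storage volume alone, however high the measured concentrations are. Everyone enrolled on the Reduced dose joined before Protocol Amendment 9, so that group depends wholly on leftover volume.

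The second part does not depend on how missing results are counted. When the rule fails, the median goes with the geometric mean. There is good reason to withhold a geometric mean built largely on LLOQ/2 substitution. That reason does not extend to the median, which does not depend on the substituted value while fewer than half the results are BLQ. BLQ results gather where exposure is low, so the cells that lose their median are most likely to be those such as high ADAb titer, where a measure of central exposure is most wanted.

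At stake are summary estimates of a primary PK variable and of its relation to ADAb, and whether two programmers would build the same table from one sentence.

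**Working it through.** The plan states no figure for this rule, so there is nothing to reproduce. The check works through what the rule does.

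**Inputs**
- Threshold two-thirds; on failure, minimum and maximum only (Section 8.1).
- 78 participants enrolled on the Original dose by Protocol Amendment 5 (Section 2.4); 163 in the 2016 interim analysis (Section 2.3); 30 added on the Original dose after Amendment 9 (Section 2.3).
- Reduced-dose count: 163 − 78 = 85. The Week 12 response rates in Section 2.3 agree: 67/85 = 78.8% and 60/85 = 70.6%; 59/78 = 75.6% and 50/78 = 64.1%.
- Re-assay yield and BLQ share: not in the SAP, so ranges are assumed.

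**Step 1. Values needed if missing results are in the denominator.** With N due, the rule needs the smallest whole number that is at least 2N/3.
- Reduced dose, all 85 assumed due: 2 × 85/3 = 56.7, so 57. With 56 results, all above the LLOQ, and 29 missing, the geometric mean is withheld. At 60% yield, 85 × 0.60 = 51 valid values would shrink to a minimum and a maximum.
- With the 20% dropout assumed in Section 2.4, 85 × 0.80 = 68 would be due, 2 × 68/3 = 45.3, so 46 are needed and 45 valid values would not be enough.
- Original dose, 78 + 30 = 108 assumed due: 72 needed. If all 30 newer participants contribute, the older samples must yield (72 − 30)/78 = 53.8%.
- A stratum of 10 (the planned Reduced-dose minimum per weight range): 7 needed, so 4 failures are enough.

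**Step 2. Missing and BLQ combined.** With yield y and BLQ share b among assayed samples, the cell is shown when y(1 − b) ≥ 2/3, that is y ≥ (2/3)/(1 − b).

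| BLQ share b | Yield needed |
|---|---|
| 0% | 66.7% |
| 10% | 74.1% |
| 20% | 83.3% |
| 30% | 95.2% |

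Above one-third BLQ, the cell fails even at full yield.

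**Step 3. Small cells.** For a cell of 10, the chance of fewer than 7 usable results (binomial) is 62%, 35%, 12% and 1% when each sample is usable with probability 0.6, 0.7, 0.8 and 0.9.

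**Step 4. The median.** Take 20 available results, none missing, 7 of them BLQ (35%). The rule needs 14 above the LLOQ (2 × 20/3 = 13.3) and there are 13, so it fails. The median is the mean of the 10th and 11th ranked values. Both are above the LLOQ, because only the seven lowest are BLQ. The same holds for any BLQ share between one-third and one-half. In a simulation with lognormal concentrations (geometric CV 50% to 150%, an assumption) and 34% or 45% BLQ, the median was 0.34 to 0.50 µg/mL and within 0.001 of the true geometric mean. That agreement follows from the lognormal shape, where median and geometric mean coincide; it shows only that BLQ at this level does not disturb the median.

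**Step 5. After the change.** With missing results out of the denominator, volume loss cannot fail the two-thirds test: if every assayed value is above the LLOQ the share is 100% at any yield, and only the minimum counts can still apply.

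**The case against.** The best reply is that the denominator is never defined. The sentence speaks of concentrations at a visit, not of samples scheduled or participants due, and Section 8.1 summarises ECLIA results only. A sample never assayed yields no concentration to count, so the words on missingness may merely say that missing values are ignored. This reading is possible. It leaves those words with no work to do, though, and they were added on purpose in Amendment 6. At the least, the sentence admits two tables. The reply also leaves the median untouched.

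The illustrative denominators are fairly challenged too. The PK-PP Set excludes anyone without a measurable ECLIA sample, Reduced-dose data stop at the first dose change, and participants drop out. So 85 is an upper illustration, and the share required is what carries over.

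Several stronger readings are tempting and do not hold:
- That the 3-value and 5-value minimums contradict the two-thirds rule. They are further conditions, and all can apply together.
- That the PK or ADAb answer is lost. Section 8.1 lists every concentration and plans spaghetti plots; Section 8.3 adds individual plots and scatter plots by ADAb class.
- That displayed results are biased upward. A withheld cell still shows its minimum and maximum, so the suppression is visible, and the SAP does not say how a withheld visit appears in the mean plots.
- That ADAb quartiles hold about 20 participants each. Section 8.2.2 gives negatives a zero titer and sends some participants to a missing class, so equal groups do not follow.

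**Conclusion.** The point holds in two parts of different strength. First, on the literal reading, missing ECLIA results count against the threshold, and a cell with no BLQ value at all loses its geometric mean once fewer than two-thirds of the results are available. This rests on missing results being in the denominator, which the wording suggests but does not state. Second, on any reading, a cell with between one-third and one-half BLQ loses a median that could still be estimated.

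A reader might infer that the Week 16 or Week 48 geometric means will in fact be blank. The SAP does not support that: it gives no re-assay yield, no BLQ rate and no PK-PP count by visit. The geometric mean is also one of several descriptive statistics for the primary variable, with no hypothesis test attached. What is at risk is a summary estimate, not the underlying data. Because the stated rule can be replaced by a better one for a little wording, it is worth changing before the final tables are programmed.

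**What to change.** In Section 8.1, apply the two-thirds criterion to the non-missing ECLIA concentrations at the visit that have not been excluded under Section 3.5. Keep the existing minimums of 3 values for summary statistics and 5 for the CI. When the criterion fails, withhold the geometric mean and CV but still report n, n (%) BLQ, the median (shown as BLQ if more than half the results are BLQ), minimum and maximum.

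The cost is a few sentences of SAP wording and slightly more content in the PK tables, with no new data. The downside is that some geometric means will come from incomplete sample sets; printing n in each cell makes that visible.

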#### 8.1.1 **ECLIA vs ELISA samples**

In line with the proportion of study participants and the proportion of PK samples with sufficient volume for re-analysis with the ECLIA method out of all PK samples initially analyzed with the ELISA method were summarized for the Updated Week 24 Interim analysis only.

First, the number and percentage of study participants with at least one PK sample reanalyzed using the ECLIA method (after previous analysis using the ELISA method) were presented. For this percentage, the denominator is the number of study participants with at least one non-missing PK result from the ELISA method, and the numerator is the number of study participants with at least one non-missing PK result from the ECLIA method that had also been analyzed with the ELISA method previously. (Below LLOQ is considered a nonmissing result.)

Second, the number and percentage of post-baseline PK samples that were re-analyzed using the ECLIA method (after previous analysis using the ELISA method) were presented. For this percentage, the denominator is the number of post-baseline PK samples with non-missing ELISA results. The numerator is the number of post-baseline PK samples with non-missing ECLIA results where the same PK sample had previously been analyzed using the ELISA method. (Below LLOQ is considered a non-missing result.)

Additionally, the proportion of study participants and the proportion of PK samples with sufficient volume for re-analysis with the ECLIA method out of all PK samples analyzed with the ECLIA method (either originally or via re-analysis) were summarized.

First, the number and percentage of study participants with at least one PK sample reanalyzed using the ECLIA method (after previous analysis using the ELISA method) were presented. For this percentage, the denominator is the number of study participants with at least one non-missing PK sample that was analyzed using the ECLIA method (either originally or via re-analysis). The numerator is the number of study participants with at least one non-missing PK result from the ECLIA method for a sample that had also been analyzed with the ELISA method previously. Also, the number and percentage of study participants that did not have any PK sample re-analyzed with the ECLIA method were presented. The denominator is the same, but the numerator is the number of study participants for whom all

non-missing PK results obtained using the ECLIA method were on samples that had never been analyzed using the ELISA method. (Below LLOQ is considered a non-missing result.)

Second, the number and percentage of post-baseline PK samples that were re-analyzed using the ECLIA method (after previous analysis using the ELISA method) were presented. For this percentage, the denominator is the number of non-missing post-baseline PK results that were obtained using the ECLIA method (either originally or via re-analysis). The numerator is the number of those non-missing post-baseline PK results that were obtained by re-analysis with the ECLIA method, after having also been analyzed by the ELISA method previously. Also, the number and percentage of those post-baseline samples that were not re-analyzed with the ECLIA method (out of those analyzed with ECLIA method) were presented. The denominator is the same, but the numerator is the number of those non-missing post-baseline PK results for samples that were only ever analyzed using the ECLIA method. (Below LLOQ is considered a non-missing result.)

All summaries were provided for the Safety Set and presented for Original CZP Dose, Reduced CZP Dose, Complete Original CZP Dose and Complete Reduced CZP Dose by baseline weight.

## 8.2 Anti-CZP antibodies

Immunogenicity will be assessed through listing of individual results by study participant and summary tables and graphs for data generated with the ECLIA method only for the SS. Immunogenicity data will be related to PK (using the PK-PP set), efficacy (using the FAS) and safety (using the SS). All data including those results at the Final Visit will be used for analyses for the entire study.

Anti-drug antibodies will be assessed by a three-tiered approach: screening (positive or negative screen), confirmatory (positive or negative immuno-depletion) and titer assays, using ECLIA methods. Cut points will be determined during assay validation and used by the bioanalytical laboratory to determine the status of ADAb in the test samples as described in Table 8–1.

Table 8-1: ADAb status at sample level

	ADAb positive	Sample values that are 'positive screen' and 'positive immuno-			
	(ADAb+)	depletion.'			
	100 V				
	ADAb negative	Sample values that are either 'negative screen' or 'positive screen' and			
	(ADAb-)	'negative immuno-depletion' if corresponding drug levels are equal or			
	, Co.	below the validated drug tolerance limit of the assay allowing detection			
	o'll'	of 100 ng/ml ADAb positive control or limit dictated by the ADAb assay			
9		and project needs (e.g. 250 ng/ml positive control).			
	ADAb negative	Sample values that are either 'negative screen' or 'positive screen' a 'negative immuno-depletion' if corresponding drug levels are equal below the validated drug tolerance limit of the assay allowing detection of 100 ng/ml ADAb positive control or limit dictated by the ADAb assay			

Table 8–1: ADAb status at sample level

ADAb inconclusive	Sample values that are either 'negative screen' or 'positive screen' and 'negative immuno-depletion' but with corresponding drug levels above the validated drug tolerance limit of the assay allowing detection of 100 ng/ml ADAb positive control or limit dictated by the ADAb assay and project needs (e.g. 250 ng/ml positive control).
Missing	Samples that were not collected per schedule or that could not be tested for ADAb status due to inadequate sample volume, mishandling, or errors in sample collection, processing, storage, etc.

Confirmed positive samples will be titrated and the titer will be reported including the minimum required dilution (MRD) of the assay.

- If the titer, for an ADAb level that is 'positive screen' and 'positive immunodepletion' status, is missing, then ADAb status will be considered as positive and no imputation rules apply for the missing titer.
- If the ADAb level is 'positive screen' but no confirmatory result could be determined, then a conservative approach will be used and ADAb status will be considered as positive. No imputation rules apply for the missing titer.

